9.4 Gender and Minority Accrual Estimates

The gender and minority distribution of the study population is expected to be:

Accrual Targets			
Ethnic Category	Sex/Gender		
	Females	Males	Total
Hispanic or Latino	8	3	11
Not Hispanic or Latino	128	136	264
Ethnic Category: Total of all subjects	136	139	275
Racial Category			
American Indian or Alaskan Native	3	0	3
Asian	3	3	6
Black or African American	14	8	22
Native Hawaiian or other Pacific Islander	3	3	6
White	113	125	238
Racial Category: Total of all subjects	136	139	275

This distribution was derived from ACNS0122.

10.0 EVALUATION CRITERIA

10.1 Common Terminology Criteria for Adverse Events (CTCAE)

This study will utilize version 4.0 of the CTCAE of the National Cancer Institute (NCI) for toxicity and performance reporting. A copy of the CTCAE version 4.0 can be downloaded from the CTEP website (http://ctep.cancer.gov/protocolDevelopment/electronic_applications/ctc.htm). Additionally, toxicities are to be reported on the appropriate case report forms.

Please note: 'CTCAE v4.0' is understood to represent the most current version of CTCAE v4.0 as referenced on the CTEP website (ie, v4.02 and all subsequent iterations prior to version 5.0).

10.2 General Methodology for Determining Tumor Measurements

2D (area) tumor dimensions are determined by measurement of the longest tumor dimension and its perpendicular for each target lesion. 3D (volume) tumor dimensions are determined by measurement of the longest tumor dimension and its perpendicular and the length (perpendicular to the plane of the axial measurement) for each target lesion. Regarding MRI imaging, the radiologist at each institution may select whatever sequence best highlights the tumor (T1 enhanced or T2 weighted or FLAIR images) and the same sequence should be used for serial measurements. Response determination will be based on a comparison of a 2D (area: $W \times T$ – see below) 3D (volume; $W \times T \times L$ – see below) between the baseline assessment and the study date designated in the follow-up Report Form. Reports for the

follow-up exams should reiterate the measurements obtained at baseline for each target lesion. Newly occurring lesions should also be enumerated in these reports.

[figure not shown]
Tumor response criteria are determined by changes in size using the longest tumor dimension, and its perpendicular +/- length. Either T1 or T2 weighted images are used - which ever gives the best estimate of tumor size. The following section describes the methodology. (See Figure 10.1 below for illustration)

1. For MRI imaging the longest diameter can be measured from the axial plane or the plane, provided the same plane is used in follow ups. This longest measurement of the tumor is referred to as the width (W).
2. The perpendicular measurements should be determined - transverse (T) measurement, perpendicular to the width in the selected plane.
3. The length is then measured as the perpendicular to the plane defined by measurements in 1 and 2.
4. The cystic or necrotic components of a tumor are typically not considered in tumor measurements. Therefore only the solid component of cystic/necrotic tumors should be measured. If cysts/necrosis composes the majority of the lesion, the lesion may not be “measurable”.

Options:

- if the cyst/necrosis is eccentric, the W and T (and L) of the solid portion should be measured, the cyst/necrosis excluded from measurement
- if the cyst/necrosis is central but represents a small portion of the tumor (< 25%), disregard and measure the whole lesion

10.3 Selection of Target Lesions

1. For most CNS tumors, only one lesion/mass is present and therefore is considered a “target” for measurement/follow up to assess for tumor progression/response.
2. In case of a bifocal lesion both lesions should be selected as “target” lesions.
3. The lower size limit of the target lesion(s) should be at least twice the thickness of the slices showing the tumor to decrease the partial volume effect (e.g. 8 mm lesion for a 4 mm slice).

10.4 Response Criteria for Target Lesions

1. Response criteria are assessed in 3 (volume) (or 2 (area) if 3 not possible) dimensions – the product of W x T x (L).
2. To assess response/progression, the ratio is calculated (x 100 = %):

$$\frac{W \times T \times (L) \text{ (current scan)}}{W \times T \times (L) \text{ (reference scan)}}$$
3. Development of new disease or progression in any established lesions is considered progressive disease (PD), regardless of response in other lesions – e.g. even when multiple lesions show opposite responses, the progressive disease takes precedence.
4. For purposes of this study, response criteria for target lesions are:

Complete Response (CR): Complete disappearance of visible disease on imaging allowing for minimal residual disease/enhancement ≤ 0.5 cm maximal dimension in suprasellar or ≤ 1 cm in pineal locations.

Continued complete response (CCR): Continuing absence of radiographically identifiable disease allowing for minimal residual disease/enhancement ≤ 0.5 cm maximal dimension in suprasellar or ≤ 1 cm in pineal locations.

Partial response (PR): > 0.5 cm dimension residual in the suprasellar area or > 1 cm residual in case of pineal involvement after completion of chemotherapy, but $\geq 65\%$ decrease in the sum of the products of the three perpendicular diameters (volume) of all target lesions (up to 5), taking as reference the initial baseline measurements.

Stable Disease (SD): Neither sufficient decrease in the sum of the products of the three perpendicular diameters of all target lesions to qualify for PR (taking as reference the initial baseline measurements), nor sufficient increase in a single target lesion to qualify for PD, (taking as reference the smallest disease measurement since the treatment started) and residual disease after chemotherapy of > 1.5 cm maximal diameter.

Progressive Disease (PD): 40% or more increase in the product of perpendicular diameters (volume) of ANY target lesion, taking as reference the smallest product observed since the start of treatment, or the appearance of one or more new lesions.

***In the circumstance that 3-D measurement cannot be determined, maximal diameter in a 2-D measurement (area) would be used to evaluate response: TxW (product of the longest diameter and its longest perpendicular diameter)**

Complete response (CR): Complete disappearance of visible disease on imaging allowing for minimal residual disease/enhancement ≤ 0.5 cm maximal dimension in suprasellar or ≤ 1 cm in pineal locations.

Continued complete response (CCR): Continuing absence of radiographically identifiable disease allowing for minimal residual disease/enhancement ≤ 0.5 cm maximal dimension in suprasellar or ≤ 1 cm in pineal locations.

Partial response (PR): > 0.5 cm maximal dimension residual in the suprasellar area or > 1 cm residual in case of pineal involvement after completion of chemotherapy, but more than $\geq 50\%$ decrease in 2-D (area) measurement.

Stable disease (SD): Decrease in $< 50\%$ of all target lesions and residual disease after chemotherapy of > 1.5 cm maximal diameter.

Progressive disease (PD): Defined as $\geq 25\%$ increase 2-D (area) of target lesion(s) or development of any new lesions irrespective of the response of the initial lesions.

5. Defining Tumor Marker Response

Patients tumor marker in serum and CSF must remain negative (AFP, hCG β) or become negative (AFP, hCG β) at completion of chemotherapy. Patients with PD and increasing levels of hCG β or AFP after completion of 2, 4 or 6 courses of chemotherapy will come off protocol.

10.5 Retrospective Response Review

MRI imaging for all patients on study will undergo retrospective central review following the completion of treatment. Results of the retrospective review will not be returned to the site. See [Section 14.4](#) for imaging central review requirements.

11.0 ADVERSE EVENT REPORTING REQUIREMENTS

11.1 Purpose

Adverse event data collection and reporting, which are required as part of every clinical trial, are done to ensure the safety of patients enrolled in the studies as well as those who will enroll in future studies using similar agents.

11.2 Determination of Reporting Requirements

Reporting requirements may include the following considerations: 1) the characteristics of the adverse event including the *grade* (severity); 2) the *relationship to the study therapy* (attribution); and 3) the *prior experience* (expectedness) of the adverse event.

Commercial agents are those agents not provided under an IND but obtained instead from a commercial source. In some cases an agent obtained commercially may be used for indications not included in the package label. In addition, NCI may on some occasions distribute commercial supplies for a trial. Even in these cases, the agent is still considered to be a commercial agent and the procedures described below should be followed.

Determine the prior experience Expected events are those that have been previously identified as resulting from administration of the agent. An adverse event is considered *unexpected*, for reporting purposes only, when either the type of event or the severity of the event is not listed in:

- ***the current known toxicities for each commercial agent as provided in the Drug Information for Commercial Agents Used by the Children's Oncology Group posted on the COG website; or***
- ***the drug package insert.***

Secondary Malignancy

A ***secondary malignancy*** is a cancer caused by treatment for a previous malignancy (eg, treatment with investigational agent/intervention, radiation or chemotherapy). A metastasis of the initial neoplasm is not considered a secondary malignancy.

All secondary malignancies that occur following treatment need to be reported via CTEP-AERS. Three options are available to describe the event:

- Leukemia secondary to oncology chemotherapy

- Myelodysplastic syndrome
- Treatment related secondary malignancy

11.3 Reporting of Adverse Events for Commercial Agents –via CTEP-AERS

Expedited AE reporting must use CTEP-AERS (Adverse Event Expedited Reporting System), accessed via <https://eapps-ctep.nci.nih.gov/ctepaers>

Commercial reporting requirements are provided in Table B. The commercial agent(s) used in this study are listed in the front of this protocol immediately following the Study Committee roster.

- COG requires the CTEP-AERS report to be submitted **within 7 calendar days** of learning of the event.
- Use the NCI protocol number and the protocol-specific patient ID provided during trial registration on all reports.

CTCAE term (AE description) and grade: The descriptions and grading scales found in the NCI Common Terminology Criteria for Adverse Events (CTCAE) version 4.0 will be utilized for AE reporting and are located on the CTEP website at:

http://ctep.cancer.gov/protocolDevelopment/electronic_applications/ctc.htm. All appropriate treatment areas should have access to a copy of the CTCAE.

Table B

Reporting requirements for adverse events experienced by patients on study who have NOT received any doses of an investigational agent on this study.

CTEP-AERS Reporting Requirements for Adverse Events That Occur During Therapy With a Commercial Agent or Within 30 Days¹

Attribution	Grade 4		Grade 5
	Unexpected	Expected	
Unrelated or Unlikely			CTEP-AERS
Possible, Probable, Definite	CTEP-AERS		CTEP-AERS

¹This includes all deaths within 30 days of the last dose of treatment with a commercial agent, regardless of attribution. Any death that occurs more than 30 days after the last dose of treatment with a commercial agent which can be attributed (possibly, probably, or definitely) to the agent and is not due to cancer recurrence must be reported via CTEP-AERS.

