15.2.3 Stratum 1 (NGGCT)

- If CR/PR after 6 cycles of induction chemotherapy, radiotherapy should commence within 3 weeks of recovery from last chemotherapy (Day 21) and no later than 6 weeks after the first day of the last chemotherapy cycle or the patient will be removed from protocol therapy (See Section 8.1).
- If PR, SD or PD after 6 cycles of induction chemotherapy, radiotherapy will not begin until after second-look surgery. Radiotherapy must begin within 31 days after surgery. If the patient has positive markers or $<$ PR after second-look surgery, they will be removed from protocol therapy. If radiotherapy is not initiated within 31 days after surgery, the patient will be removed from protocol therapy.

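### Expedited adverse-event reporting runs only to 30 days after the last drug dose, so for most permitted start dates at least half of radiotherapy is given after it ends

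*Combined protocol and SAP*

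**What the plan says.** Section 11.3 requires a CTEP-AERS report within 7 calendar days for the events marked in Table B. The table is headed "CTEP-AERS Reporting Requirements for Adverse Events That Occur During Therapy With a Commercial Agent or Within 30 Days". Section 11.3 also says which agents are meant: "The commercial agent(s) used in this study are listed in the front of this protocol immediately following the Study Committee roster". That list is carboplatin, etoposide, ifosfamide, filgrastim and mesna.

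Within the window, every death is reportable whatever its cause, and so is an unexpected Grade 4 event that is at least possibly related. After the window, footnote 1 covers only deaths, and only some of them: "Any death that occurs more than 30 days after the last dose of treatment with a commercial agent which can be attributed" to the agent, provided that the death is not due to recurrence. Section 11.2 adds a separate rule without a time limit: "All secondary malignancies that occur following treatment need to be reported via CTEP-AERS". Its definition includes malignancies caused by radiation.

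Radiotherapy follows the last induction cycle. Section 15.2.3 (Stratum 1) has it start after recovery, which it places at Day 21, and "no later than 6 weeks after the first day of the last chemotherapy cycle". Section 15.2.4 sets the same limit for Stratum 2. After second-look surgery, Section 15.2.3 says: "Radiotherapy must begin within 31 days after surgery".

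**The concern.** Reduced radiotherapy is what Stratum 1 tests and part of what Stratum 2 tests, yet the expedited clock is set by the drugs that precede it. Radiotherapy has no reporting window of its own. As written, an unexpected Grade 4 event late in radiotherapy, or a later death attributed to radiotherapy or second-look surgery alone, starts no 7-day clock.

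The protocol has no numeric toxicity stopping rule that would act instead. The accrual-suspension triggers in Sections 9.3.1 and 9.3.2 (9 and 7 failures) count progression and loss to follow-up, not toxicity. What is at stake is how quickly a serious single event reaches people who can act on it. The primary analysis and its operating characteristics are not affected.

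**Working it through.** **Fractions (Sections 15.6.2 and 15.6.3): dose divided by dose per fraction.**
- Stratum 1: 3060/180 = 17 and 2340/180 = 13, total 30.
- Stratum 2: 1800/150 = 12 and 1200/150 = 8, total 20. At 36 Gy: 2400/150 = 16, plus 8, total 24.

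These agree with the fraction numbers in the protocol.

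**End of window: day of last dose in the last cycle plus 30 (dosing days from Section 4.1).**
- Stratum 1, last ifosfamide, etoposide and mesna on Day 5: 5 + 30 = Day 35.
- Stratum 1, filgrastim to Day 15: 15 + 30 = Day 45.
- Stratum 2, last etoposide on Day 3: 3 + 30 = Day 33.

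**Start of radiotherapy.** The earliest start is taken as Day 22, the day after the 21-day cycle. The latest is six weeks after Day 1: 1 + 42 = Day 43. Fractions are given Monday to Friday (Section 15.2.5).

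**Worked count, Day 1 a Monday, start Day 22.** Treatment days are 22–26, 29–33, 36–40, 43–47 and so on.
- Window to Day 35: 5 + 5 = 10 fractions inside, 30 − 10 = 20 outside.
- Window to Day 45: 5 + 5 + 5 + 3 = 18 inside, 30 − 18 = 12 outside.
- Window to Day 33: 5 + 5 = 10 inside, so 20 − 10 = 10 or 24 − 10 = 14 outside.

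**Fractions outside the window.** Ranges cover Day 1 falling on any weekday from Monday to Friday.

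| Case | Window ends | Start Day 22 | Day 29 | Day 36 | Day 43 |
|---|---|---|---|---|---|
| Stratum 1, cytotoxic anchor, 30 fractions | Day 35 | 20 | 25 | 30 | 30 |
| Stratum 1, filgrastim to Day 15, 30 fractions | Day 45 | 12–14 | 17–19 | 22–24 | 27–29 |
| Stratum 2, 20 fractions | Day 33 | 10–12 | 15–17 | 20 | 20 |
| Stratum 2, 24 fractions | Day 33 | 14–16 | 19–21 | 24 | 24 |

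On the filgrastim anchor, more than half of the fractions are outside for every start from Day 28 on. On the other anchors, at least half are outside for every start from Day 22.

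**With the window re-anchored.** Adding 30 days to the last fraction, for starts from Day 22 to Day 43, gives a window ending about Day 91–114 in Stratum 1, and Day 77–100 (20 fractions) or Day 83–106 (24 fractions) in Stratum 2. Every fraction then lies inside.

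**The case against.** The strongest answer is that several routes remain.

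- **Deaths.** A reader might infer that radiotherapy-related deaths have no expedited route at all. The documents do not support that. Deaths within 30 days of the last dose are reportable regardless of cause, and secondary malignancies, including those due to radiation, at any time. After 30 days, a death qualifies if it is one "which can be attributed (possibly, probably, or definitely) to the agent and is not due to cancer recurrence must be reported via CTEP-AERS". A death judged possibly related to earlier chemotherapy would therefore still be caught.
- **Share of radiotherapy.** A reader might also infer that most of radiotherapy always falls outside. That is not so either. Filgrastim is on the agent list. With doses to Day 15 and a Day 22 start, 16 to 18 of the 30 Stratum 1 fractions are inside. Section 5.1.4 allows filgrastim in later Stratum 2 cycles after slow count recovery, which would lengthen that window too.
- **Expectedness.** Section 11.2 judges this against "the current known toxicities for each commercial agent as provided in the Drug Information" and the package insert, which might suggest that radiotherapy events cannot be classified. In fact, an event not listed there counts as unexpected, which is the more inclusive class.
- **Slower routes.** Section 11.4 puts all Grade 3 and higher events on case report forms. Section 12.2 sends an unexpected frequency of serious events to the data monitoring committee, and any group member may raise a concern. The form submission schedule is posted elsewhere, so the speed of routine reporting cannot be judged here.
- **Main safety question.** Objective 1.1.1 measures safe reduction by progression-free survival and patterns of failure, which have their own triggers.

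All of this stands, and it narrows the point. It does not close the gap: none of these routes puts a deadline on a single unexpected Grade 4 event, or on a death due only to radiotherapy or surgery, once the 30 days have passed.

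**Conclusion.** The gap is real but bounded. More than 30 days after the last commercial-agent dose, unexpected Grade 4 events and deaths attributed only to radiotherapy or second-look surgery, other than secondary malignancies, have no 7-day route. For most permitted start dates that period holds at least half of radiotherapy, and for late starts nearly all or all of it.

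The counts assume no interruptions or holidays and, in Stratum 2, no filgrastim. A Day 21 start would move any count by at most one fraction. Radiotherapy after a post-induction second-look operation is likely to fall largely outside, but the documents give no interval from chemotherapy to surgery, so this cannot be counted. Surgery during induction can fall inside the window. In Stratum 2, radiotherapy is only part of the regimen under test, which also includes simplified chemotherapy.

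This is an inexpensive safety improvement. No estimate or decision rule changes because of it.

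**What to change.** In Section 11.3, Table B and footnote 1:

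1. Replace the reference to therapy with a commercial agent by *protocol therapy (chemotherapy, protocol second-look surgery and radiotherapy)*.
2. Run the 30 days from the last protocol therapy of any kind.
3. Make later deaths reportable when possibly, probably or definitely attributable to any protocol therapy.

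Leave the secondary-malignancy rule as it is. Do not add a list of expected radiotherapy events to Section 11.2. Events on such a list would become expected, and Table B asks for no expedited report of an expected Grade 4 event, so the list would narrow reporting.

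The cost is a wording amendment and a small number of extra expedited reports from sites. Treatment, endpoints and sample size are untouched.

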11.4 Routine Adverse Event Reporting

Note: The guidelines below are for routine reporting of study specific adverse events on the COG case report forms and do not affect the requirements for CTEP-AERS reporting.

The NCI defines both routine and expedited AE reporting. Routine reporting is accomplished via the Adverse Event (AE) Case Report Form (CRF) within the study database. For this study, routine reporting will include all toxicities reported via CTEP-AERS and all Grade 3 and higher Adverse Events.

12.0 STUDY REPORTING AND MONITORING

The Case Report Forms and the submission schedule are posted on the COG web site with each protocol under “*Data Collection/Specimens*”. A submission schedule is included.

12.1 CDUS

This study will be monitored by the Clinical Data Update System (CDUS). Cumulative CDUS data will be submitted quarterly to CTEP by electronic means. Reports are due January 31, April 30, July 31 and October 31. This is not a responsibility of institutions participating in this trial.

12.2 Data and Safety Monitoring Committee

To protect the interests of patients and the scientific integrity for all clinical trial research by the Children’s Oncology Group, the COG Data and Safety Monitoring Committee (DSMC) reviews reports of interim analyses of study toxicity and outcomes prepared by the study statistician, in conjunction with the study chair’s report. The DSMC may recommend the study be modified or terminated based on these analyses.

Toxicity monitoring is also the responsibility of the study committee and any unexpected frequency of serious events on the trial are to be brought to the attention of the DSMC. The study statistician is responsible for the monitoring of the interim results and is expected to request DSMC review of any protocol issues s/he feels require special review. Any COG member may bring specific study concerns to the attention of the DSMC.

The DSMC approves major study modifications proposed by the study committee prior to implementation (eg, termination, dropping an arm based on toxicity results or other trials reported, increasing target sample size, etc.). The DSMC determines whether and to whom outcome results may be released prior to the release of study results at the time specified in the protocol document.

13.0 SURGICAL GUIDELINES

Timing of protocol therapy administration, response assessment studies, and surgical interventions are based on schedules derived from the experimental design or on established standards of care. Minor unavoidable departures (up to 72 hours) from protocol directed therapy and/or disease evaluations (and up to 1 week for surgery) for valid clinical, patient and family logistical, or facility, procedure and/or anesthesia scheduling issues are acceptable per COG administrative Policy 5.14 (except where explicitly prohibited within the protocol).

13.1 Pre-operative Considerations

The majority of patients with primary intracranial germinoma or NGGCT will present with mass lesions in either the pineal and/or suprasellar regions. Other less common locations include the thalamus/basal ganglia and fourth ventricle. Patients with primary tumors in the pineal region are likely to present with hydrocephalus. The neurosurgeon must consider the following goals in the initial management of patients suspected of harboring a primary germ cell tumor.

